9.4.1.3. Norwegian Health Registries

The Norwegian Prescription Database (NorPD) includes data on all prescription drugs dispensed in Norway since January 1, 2004 and is controlled by the Norwegian Institute of Public Health (NIPH). Pharmacies electronically register prescriptions to the NorPD via Statistics Norway on a monthly basis. The residents' national ID number and the prescribing provider's ID number are

replaced by a pseudonym to link drug use to individuals and other registries data while protecting patient identity. The NorPD will be linked with other Norwegian Patient Registries with information that includes demographic information of the patient (sex, year of birth, and municipality of residence), place and time of treatment, diagnoses, medical procedures, and reimbursement information of medical care.

Based on current and projected Mysimba prescription counts as estimates obtained during the last annual feasibility assessment and reimbursement in Norway restricted to the morbidly obese, we anticipate that this database may include >3,000 new users of Mysimba who will be eligible for inclusion in the study as of December 31, 2023 (to be confirmed when data access is granted). A final analysis of the database will be conducted for the final report including all patients meeting the inclusion criteria for the study as of 31 December 2024 (final report available 31 December 2025).

9.4.1.4. Swedish National Registries

The Swedish Statistical Database for Medicinal Products contains data on all prescription drugs dispensed by pharmacies in Sweden from 2006 – 2020. The registry includes medications and any accompanying consumable products (e.g., food for special nutrition for children under 16 years of age) dispensed to residents of the Kingdom. Included among the data is information on patient information (gender, age, location), product information such as ATC classification codes, pharmaceutical names, and quantity dispensed, when medications were prescribed, costs, and healthcare provider information of who prescribed the drug. These data will be linked with the Swedish Inpatient Registry (or Hospital Discharge Register), which provides data on physical and psychiatric inpatient and hospital-based outpatient care, along with patient related data (including age, sex, county of residence), hospital and department the patient visited, timing and duration of hospitalization and discharge, medical diagnoses, procedures, and psychiatric care.

Based on current and projected Mysimba prescription counts and the lack of reimbursement of Mysimba in Sweden, we anticipate that this database will include > 750 new users of Mysimba who would be eligible for inclusion in the study as of December 31, 2023. Actual counts will be available with the first interim report. Analysis of the database will be conducted for the final report if there are >750 eligible patients at the time of interim or final analyses.

9.4.2. United States Data Source

An EHR or claims-based integrated database across multiple healthcare systems in the United States, providing a representative mix of US Commercial Insurance and Medicare (major systems of health insurance in the US) has been selected. Arcadia Data Research was chosen as the US data for this study because of their approximately ten-year history of successfully curating data for health systems that are substantially involved in value-based care, which necessitates high-quality clinical data across the included patient populations. Data incorporated into the US dataset will include electronic medical records from multiple systems, laboratory test orders, and prescription data. Moreover, a sizeable proportion of the EHR population will also have their health insurance claims records linked in their final (adjudicated) form. The typical data extract will include (but is not limited to): patient demographics and characteristics (including height and weight or BMI if available), medical encounters, appointments, provider data, charges, assessments, immunizations, health maintenance and medical history, laboratory orders/results, vital signs (e.g., blood pressure, heart rate), patient insurance, prescriptions and active medications, problem lists, and patient allergy information. EHR data are sourced from large integrated delivery networks, academic medical centres, ambulatory care, primary care, core hospitals, and others. The data are coded in standard vocabularies used within the US, including ICD-10, NDC, CPT, LOINC, etc. Additional information, such as social determinants of health will be captured, if available. The data are expected to contain sufficient information to elucidate occurrence and determine levels of all variables, with the following exceptions which may be prone to misclassification due to limited coding in administrative and clinical data: neuropsychiatric conditions, history or current substance use or dependence, breastfeeding status, and reason(s) for medication discontinuation.

The integration of claims data for a subset of patients will be important for this study in order to capture pharmacy prescriptions dispensed and for better capture of MACE events. The selected database will be described in more detail in the US SAP.

We anticipate that the US dataset will include >20,000 new users of Contrave who will be eligible for inclusion in the study as of December 31, 2022. The final analysis of the US database will be conducted and presented in a US only study report.

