9.1.1. Inclusion Criteria

Patients will be included in the study if they meet the following inclusion criteria:

- 1. At least one prescription of Mysimba/Contrave in his/her medical records any time during the study period (US) OR at least one dispensing of Mysimba/Contrave in his/her registry any time during the study period (Nordic);
- 2. At least 365 days of computerized records prior to first Mysimba/Contrave prescription or dispensing date; and 3Patient is active (i.e., alive and registered/accruing data) at the time of the first Mysimba/Contrave prescription or dispensing date.

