9.1.2. Exclusion Criteria

All patients meeting inclusion criteria will be included in the study; no exclusion criteria will be applied.

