9.7. Data Analysis

9.7.1. Timing of Feasibility, Interim, and Final Analyses

Prior to study start, feasibility was conducted annually.

One cohort per country will be extracted each time the database is opened. Per database, the following analyses will be conducted:

- 1. ongoing data review, for each of the participating Nordic countries
- 2. a first (interim) analysis when a database size reaches 750 patients with up to 548 days of activity in database after index date
- 3. a second (interim) analysis when an additional 2,250 patients (total 3,000 patients) with a Mysimba/Contrave index date are included in a database with up to 548 days of calendar time available in the database after the index date
- 4. a final analysis of the database will be conducted for the final report including all patients from the EU data sources meeting the inclusion criteria for the study as of 15 February 2025. If >3000 patients are available at the time of an interim analysis, the final report for

that database will be submitted one year after data is accessible. If final data is available 31 Dec 2024, the final report will be submitted by 31 Dec 2025.

All analyses will be performed separately in each country. All patients in the study will be included in the analysis, regardless of whether there is evidence of any contact with the health system (as registered by any data in the database) after inclusion into the study. One interim and one final analysis will be conducted per country. A final report will be generated when the last database in the study conducts the final analysis (when the last database has >3000 Mysimba patients, or 31 Dec 2025, whichever comes first). The final analysis from the four participating Nordic countries will be included in that report which will be accompanied by synthesis of findings, discussion, and interpretation across all Nordic databases.

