9.7.3. Incidence Rate of AESIs

The incidence rate of AESIs per person-years of exposure after initiation of Mysimba/Contrave will be assessed. Person-time of exposure will be calculated as the duration from the index date through the date of last Mysimba/Contrave prescription or dispensation (i.e., total treatment duration of Mysimba/Contrave), as applicable, plus 4 weeks. The number of cycles of Mysimba/Contrave during the exposure period will be summarized comparing all users, irrespective of their treatment duration status.

For each type of AESI, the crude incidence of new AESIs will be reported and the incidence proportion and 95% CI of will be estimated as the number of patients experiencing each type of event during Mysimba/Contrave exposure divided by the number of patients initiating treatment with Mysimba/Contrave. The proportion will be reported per 1,000 persons. The incidence density rate and 95% CI of AESI will be reported per 1,000 per person-years, using the sum of the person-years of the at-risk population as the denominator.

Further, clinical events of interest that might be associated with the occurrence of a potential AESI (e.g., newly initiating anti-epileptic/seizure medication, newly initiating medications indicated for mania or depression) will also be tabulated. For hepatotoxicity, liver function tests can be used (when available) in addition to diagnostic codes.

For reason(s) patients who discontinue treatment (i.e., do not refill their prescription), clinical events and health status occurring within the 90-day window prior to discontinuation will be summarized.

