Cardiovascular-related	Partial	Partial	Partial	Partial	Partial
death	1 artiar	1 artiar	1 artiai	1 artiar	1 artiar
Non-fatal myocardial	Yes	Yes	Yes	Yes	Yes
infarction					
Non-fatal stroke	Yes	Yes	Yes	Yes	Yes
Use of naltrexone (other	Yes	Yes	Yes	Yes	Yes
than Mysimba)	Vaa	Vaa	Vac	Vac	Vaa
Use of bupropion (other than Mysimba)	Yes	Yes	Yes	Yes	Yes
, , , , , , , , , , , , , , , , , , , ,	Vac	Vac	Vac	Vac	Yes
Use of CYP2B6 inhibitor	Yes	Yes	Yes	Yes	
Use of CYP2B6 inducer	Yes	Yes	Yes	Yes	Yes
Use of CYP2B6 substrate	Yes	Yes	Yes	Yes	Yes
Use of CYP2Db substrate	Yes	Yes	Yes	Yes	Yes
Use of medicine that lowers	Yes	Yes	Yes	Yes	Yes
seizure threshold	Vac	V	V.	V	Var
Opioid or opiate agonist	Yes	Yes	Yes	Yes	Yes
prescription or dispensing					

MAOI prescription or	Yes	Yes	Yes	Yes	Yes
dispensing	1 05	1 05	1 05	1 05	105
Pregnancy	Yes	Limited	Limited	Limited	Limited
Breastfeeding	Limited	Limited	Limited	Limited	Limited
Death	Partial	Yes	Yes	Yes	Yes
Disenrollment	Partial	Partial	Partial	Partial	Partial
Socioeconomic data		Partial	Partial	Partial	Partial
Laboratory results	Limited	Limited	Limited	Yes	Limited
Surgical procedures	Yes	Yes	Yes	Yes	Yes
Diagnostic testing results	Limited	Limited	Limited	Yes	Limited
Indication (reason) for	Partial				
treatment with Mysimba					
Discontinuation and date of	Calculated	Calculated	Calculated	Calculated	Calculated
discontinuation of					
Mysimba					
Reason(s) for treatment	Partial-no				
discontinuation	attribution				
Discontinuation due to	Partial-no				
adverse event	attribution

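### US MACE incidence is taken over all initiators, although section 9.4.2 says linked claims improve MACE capture and only a subset is linked; the rate is likely understated by an unknown amount

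*Protocol*

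**What the plan says.** - **Linkage (protocol 9.4.2).** The US source is an EHR database in which "a sizeable proportion of the EHR population will also have their health insurance claims records linked in their final (adjudicated) form". Later the section describes this linkage, which covers only part of the cohort, as "important for this study in order to capture pharmacy prescriptions dispensed and for better capture of MACE events". The linked share is not given.
- **Who enters (9.1.1, 9.1.2).** A US patient qualifies through a prescription in the medical record plus 365 days of prior records and active status. Claims linkage is not a condition, and "no exclusion criteria will be applied".
- **Who is analysed (9.7.1).** "All patients in the study will be included in the analysis, regardless of whether there is evidence of any contact with the health system" after inclusion.
- **Denominators (9.7.3).** The AESI incidence proportion is divided by the number of initiators. The incidence rate is formed "using the sum of the person-years of the at-risk population as the denominator". MACE is an AESI in sections 8 and 9.3.2.
- **Availability (Appendix 3, a draft).** US non-fatal myocardial infarction and "Non-fatal stroke" are rated Yes without qualification. US cardiovascular death, all-cause death, disenrollment, enrolment date and dispensing are rated Partial.
- **Other relevant text.** Section 9.7.3.1 allows sensitivity analyses of AESI definitions if the data permit. Section 9.4.2 leaves fuller description of the database to the US SAP. Section 9.9 does not mention incomplete MACE capture in unlinked patients.

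**The concern.** If claims improve MACE capture, capture is poorer without them. An infarction or stroke treated outside the contributing health systems would appear in the claims of a linked patient but could be missed in an unlinked one, whose person-time still counts. Pooling the two groups mixes a more complete with a less complete numerator over one common denominator, and missed events can only lower the result.

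The US cohort is the largest expected in the study (more than 20,000 new users, section 9.4.2). Its MACE rate will therefore have a narrow confidence interval, and that interval reflects sampling error only. A rate that is too low and looks precise is falsely reassuring in a safety study. The contrast of users compliant and non-compliant with the SmPC would also be affected if the linked share differed between those groups. The documents do not say whether it does.

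**Working it through.** The protocol states no MACE rate, linked share or capture sensitivity, so there is no planned figure to reproduce. The direction follows from the text. The size can only be illustrated.

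**Step 1. Does any provision separate linked from unlinked patients for MACE?** Entry does not require linkage (9.1.1), nothing excludes unlinked patients (9.1.2), all are analysed (9.7.1), and both AESI denominators are general (9.7.3). The conditional analyses in 9.7.3.1 vary how an AESI is defined, not whose events can be seen. The answer is no.

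**Step 2. Does censoring remove the problem?** Section 9.3.2 censors at death, disenrollment, 548 days or end of study. Exposed person-time in 9.7.3 runs to the last prescription plus 4 weeks, so a patient contributing to it has been prescribed the drug within a contributing system. That limits the effect of complete loss of contact. It does not help a patient who remains in view but is treated elsewhere for the event.

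**Step 3. Formula.** Let f be the linked share (of patients for the proportion, of person-time for the rate) and s the capture in unlinked relative to linked patients. Assume equal true risk in both groups, no false-positive events and complete capture in linked patients. Then

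observed/true = f + (1 − f)s, and relative shortfall = (1 − f)(1 − s).

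**Step 4. Assumed inputs** (f 0.3 to 0.9, s 0.5 to 1.0; none is in the documents):

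| f | s | observed/true | shortfall |
|---|---|---|---|
| 0.3 | 0.5 | 0.3 + 0.7 × 0.5 = 0.65 | 35% |
| 0.5 | 0.7 | 0.5 + 0.5 × 0.7 = 0.85 | 15% |
| 0.7 | 0.9 | 0.7 + 0.3 × 0.9 = 0.97 | 3% |
| 0.9 | 0.9 | 0.9 + 0.1 × 0.9 = 0.99 | 1% |
| any | 1.0 | 1.00 | 0% |

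**Step 5. Effect on the interval.** Take N = 20,000 and an assumed true risk of 5 per 1,000, with Wald 95% intervals p ± 1.96 √(p(1 − p)/n). The all-initiator analysis uses n = 20,000 and the linked analysis n = 20,000f.

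| f, s | all initiators, per 1,000 | linked only, per 1,000 |
|---|---|---|
| 0.3, 0.5 | 3.25 (2.46 to 4.04) | 5.0 (3.22 to 6.78) |
| 0.5, 0.7 | 4.25 (3.35 to 5.15) | 5.0 (3.62 to 6.38) |
| 0.7, 0.9 | 4.85 (3.89 to 5.81) | 5.0 (3.83 to 6.17) |

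In the first scenario the all-initiator interval excludes the assumed true value. In the third the difference is negligible.

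**Step 6. Is the linked subset large enough?** The 3,000 patients of section 9.5 are reached at f = 3,000/20,000 = 0.15, before any loss from requiring claims coverage. At the same risk, the interval widens by 1/√f: about 1.8 times at f = 0.3 and 1.4 times at f = 0.5.

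**The case against.** The strongest reply is that this is detail for the US SAP, which is not at hand, and that 9.7.3.1 already provides for sensitivity analyses. The US SAP may indeed add a linked analysis. But what 9.4.2 defers is the description of the database, while the entry rule and the denominators are fixed in the protocol.

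Several stronger readings are tempting, and the documents do not support them.

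- **That claims are needed to capture US MACE.** Section 9.4.2 says only that they are important and improve capture. It also leaves MACE off its list of variables prone to misclassification. The EHR sources include integrated networks and core hospitals, so hospital care is not outside the data by design.
- **That the rate is shown to be low by a definite amount.** Inputs of f 0.3 to 0.6 and s 0.5 to 0.7 would give a shortfall of 12% to 35%, but they leave out the mild cases. Nothing in the text rules out a shortfall near zero.
- **That the US rate will dominate the study's conclusions.** Analyses are run separately by country (9.7.1), US results go into a US-only report (9.4.2), and the planned synthesis is Nordic. The US is the largest cohort, no more than that.
- **That unfilled prescriptions are an overlooked flaw.** Section 9.9.1 already names them as a limitation.
- **That Appendix 3 misstates US MACE throughout.** It is a draft, its legend gives Yes the modest meaning of likely to be available, and cardiovascular death is already Partial. What remains is that the appendix reflects incomplete availability for dispensing but leaves infarction and stroke unqualified.

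**Conclusion.** The point stands in limited form. The protocol acknowledges better MACE capture in a linked subset, takes US MACE incidence over everyone, and plans no analysis by linkage status. The US MACE rate is therefore likely understated. The direction rests on capture being poorer without claims, which 9.4.2 implies, and on similar true risk in linked and unlinked patients, which is assumed.

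The size cannot be determined from the documents. The range of 0% to 35% describes assumed inputs only and is not an estimate. Distortion of the comparison by SmPC compliance is possible, but depends on a difference in linkage that nothing in the protocol establishes.

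**What to change.** 1. In 9.7.3, prespecify a US MACE analysis in the claims-linked subset, counting person-time only while the patient is claims-covered, and show it beside the all-initiator result.
2. Report the linked share and the MACE rate by linkage status.
3. In Appendix 3, qualify the US infarction and stroke entries, for example as Yes for claims-linked patients and Partial for EHR-only patients.
4. In 9.9, name incomplete MACE capture in unlinked patients as a limitation.

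Whether the linked analysis is primary or a sensitivity analysis can be left to the sponsor. The exposure definition need not change for MACE alone; doing so would give MACE a different time at risk from the other AESIs.

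The cost is one further analysis set and table, from data already in the planned extract. The linked-only interval is wider by about 1/√f, and linked patients may differ in insurance mix, which is a reason to keep both results in view.

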9.5. Study Size and Statistical Power

In the final report from each data source, the study will include data from approximately 3,000 patients per database. Based on the safety profile of bupropion, a sample size of 3,000 with no events of an outcome enables 95% confidence that the chance of that outcome is at most 3 in 3000 (i.e., 1/1000 or 0.1%). As an example, within the integrated summary of safety and effectiveness for Contrave, 13.7% of patients had a treatment emergent adverse event (TEAE) and 0.1% had a treatment emergent serious adverse event (SAE) of hypersensitivity reaction/skin rash (ISS table 2-82). Having 3,000 patients in each database would yield approximately 411 patients with this TEAE and 3 patients SAE. The confidence intervals around both percentages will be approximately 2.5%.

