4. SYNOPSIS

Title:	Drug Utilisation and Safety Study of Mysimba in Europe and Contrave in the United States
Purpose:	Results from this study will add further definition and clarity to the overall safety profile of Mysimba/Contrave, to inform the MAH's view on the following: 1. to further refine the risk management and pharmacovigilance planning for this product; and 2. to determine whether the SmPC should be revised, based on the available post-marketing evidence, with the objective of optimizing the safe and effective use of the product.
Objectives and Endpoints:	The primary objectives of the study are: 1. To describe demographic and baseline characteristics of patients initiating use of Mysimba/Contrave. 2. To evaluate patterns of Mysimba/Contrave initiation and use, including estimating the number and percentage of patients compliant and non-compliant with the SmPC. The secondary objectives of this study are: 3. To assess and compare the observed incidence of AESIs in usual clinical practice among users of Mysimba/Contrave compliant and non-compliant with the SmPC. 4. To assess the proportions of patients in the following groups who are at increased risk for AESI and to describe the characteristics of the patients with AESI for all users: a. Any user of Mysimba/Contrave; b. Users compliant with SmPC; and c. Users out of compliance with SmPC, as described above. 5. To assess the duration of Mysimba/Contrave use. 6. To identify to the extent possible within the data sources: o Initial titration scheme and proportion aligned with SmPC; o Dose adjustment in special populations and proportion aligned with SmPC; o Reasons for treatment discontinuation; and o AESIs that may have led to treatment discontinuation.
Population:	Users of Mysimba/Contrave with at least 365 days of computerized records prior to first use in Denmark Finland, Norway and Sweden, and other countries (if meeting the threshold for patients and agreed upon

Power and Sample Size:	between EMA and MAH) with sufficient uptake of Mysimba/Contrave in the respective national health systems. Additionally, U.S. data will be included. The study will include data from approximately 3,000			
rower and Sample Size.	patients per database. Only databases with at least 750 patients will be included in the analysis.			
Anticipated Study Duration:	3 years (based on current uptake in Denmark, Finland, Norway, and Sweden); study follow-up of 18 months			
Treatment:	Mysimba/Contrave			

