6. MILESTONES

Milestone	Nordic Registries Study	U.S. Study	
	Anticipated Dates	Anticipated Dates	
Study protocol resubmitted to EMA	November 21, 2022	November 21, 2022	
Protocol approved by EMA	December 15, 2022*	December 15, 2022*	
Registration in EU PAS Register	January 15, 2023	January 15, 2023	
Apply for registry data for secondary	September 15, 2023 (post	N/A	
use	EC approval)		
Data receipt and start date for data	December 29, 2023	February 15, 2023	
analysis			
Interim report of study results #1**	April 15, 2024	N/A	
Interim report of study results #2***	April 15, 2025	N/A	
Final report of study results****	December 31, 2025**	August 4, 2023**	

^{*} Subsequent dates are dependent on timing of protocol approval by EMA

^{**} Based on counts of patients prescribed/dispensed Mysimba/Contrave through the end of 2021 and assuming both 80% are captured in the databases and 80% of identified patients are new users with at least 365 days continuous eligibility in data source before first Mysimba/Contrave prescription/dispensing, then there should be >3,000 eligible patients in data sources from US, Norway, Finland and possibly Sweden in this

analysis; it is uncertain at this time whether there will be at least 750 patients in Denmark during the conduct of the NB-451 study. Data for this interim study report will be the data available by December 29, 2023; it is likely that data will only be available through 2021 at this time.

*** A second interim report will only be included if Denmark identifies 750-3,000 eligible patients who would be available before December 31, 2024.

**** Final report date dependent on accumulation of data from the four Nordic country databases. Based on counts to date and projections of new users, there should be >3,000 eligible patients in the Norway and Finland data sources at the end of 2023. The 2023 data from Norway and Finland are expected to be available in late 2024. If final data are available in late 2024, the December 2025 final report will include the new final results from Norway, Finland, and Sweden, with updated interim or final analyses in Denmark, if appropriate.. Additionally, the final report will provide synthesis across all four Nordic data sources.

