9.4.1.2. Finnish National Registries

The Finland Prescription Register includes data on prescription drugs that were reimbursed through the National Health Insurance Scheme since 2008. The data includes the medicines and corresponding products that have been purchased and reimbursed. The data are classified via the ATC system. Additionally, data will come from the Finnish Care Register for Health Care, which includes data on inpatient care as well as outpatient care. This includes data such as patient identification number, municipal residence, admission and discharge dates, diagnoses, any treatments provided, reason for seeking care, and medical procedures. Finland has other registries that capture social welfare services. All registries can be linked to the Population Register Centre, which contains demographic data on Finnish residents.

This data source was included at the request of the EMA.

Based on current and projected Mysimba prescription counts from the feasibility assessment, restriction of reimbursement of Mysimba to morbidly obese in Finland and assuming patients obtain approximately 6 Mysimba dispensings, 80% of patients are captured in databases and 80% of identified patients are new users with at least 365 days continuous eligibility in data source before first Mysimba prescription/dispensing, we anticipate having more than 750 new users of Mysimba who would be eligible for inclusion in the study as of December 31, 2023. Actual counts will be obtained at the time of the first interim report. Analysis of the database will be conducted at the time of interim analyses or final analysis if >750 patients are eligible for study inclusion, which is expected.

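### Section 9.5 gives one confidence-interval figure for a 13.7% and a 0.1% event that fits only the former, and offers 3,000-patient precision although databases are admitted from 750.

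*Protocol*

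**What the plan says.** Section 9.5 (Study Size and Statistical Power) says that in the final report from each data source "the study will include data from approximately 3,000 patients per database". It offers two illustrations at that size.

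- A zero-event bound: "a sample size of 3,000 with no events of an outcome enables 95% confidence that the chance of that outcome is at most 3 in". The denominator is the sample size, so the bound is 0.1%.
- Two hypersensitivity/skin-rash rates from the product's integrated safety summary: "13.7% of patients had a treatment emergent adverse event (TEAE) and 0.1% had a treatment emergent serious adverse event (SAE"). These are turned into about 411 and 3 patients. The section then closes: "The confidence intervals around both percentages will be approximately 2.5" percent. It does not say whether this is a full width or a half-width.

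On database size, other places in the protocol say:

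- Section 4 (Synopsis): "Only databases with at least 750 patients will be included in the analysis".
- Section 6 (Milestones), footnote on the first interim report: "then there should be >3,000 eligible patients in data sources from US, Norway, Finland and possibly Sweden". The footnote on the final report again expects more than 3,000 in Norway and Finland at the end of 2023.
- Section 9.4.1.1 (Denmark): more than 750 eligible new users by 31 December 2023 are not anticipated. The data are analysed if that number is passed.
- Section 9.4.1.2 (Finland): "we anticipate having more than 750 new users of Mysimba" by the same date.
- Section 9.4.1.4 (Sweden): "we anticipate that this database will include > 750 new users of Mysimba", again by that date.
- Section 9.7.1: the final report follows when the last database passes 3,000 patients or on 31 December 2025, whichever is earlier.

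**The concern.** The width of an interval for a proportion depends on the proportion itself. One figure cannot describe both 13.7% and 0.1%, which differ 137-fold, at the same sample size. An interval 2.5 points wide and centred on 0.1% would run below zero.

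The second difficulty is that all the precision in section 9.5 is tied to 3,000 patients, while the protocol lets a database of little more than 750 reach the final report. A reader of section 9.5 would expect the 1-in-1,000 bound from every database reported. For a smaller one it is not available, and the protocol does not say what is.

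**Working it through.** **Inputs.** From section 9.5: n = 3,000, p = 13.7% and p = 0.1%. From section 4: minimum n = 750. Two-sided 95% intervals are used, as in section 9.7.2. The zero-event bound is one-sided 95%.

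**Figures in section 9.5 that reproduce**

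- Expected counts: 3,000 × 0.137 = 411 and 3,000 × 0.001 = 3.
- Zero-event bound: 1 − 0.05^(1/3000) = 0.0998%, in line with 3/3,000 = 0.1%.

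**Interval for 13.7% at n = 3,000**

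- Standard error: √(0.137 × 0.863 / 3,000) = 0.00628. Half-width: 1.96 × 0.00628 = 1.23 points. Full width: 2.46 points.
- Exact (Clopper-Pearson) for 411/3,000: 12.49% to 14.98%, width 2.49. Wilson: width 2.46.
- So 2.5 is reproduced as a full width and not as a half-width.

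**Interval for 0.1% at n = 3,000 (3 events)**

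| Method | Full width (points) |
|---|---|
| Wald | 0.23 |
| Wald, continuity-corrected | 0.26 |
| Wilson | 0.26 |
| Exact (0.02% to 0.29%) | 0.27 |
| Wald at the 99% level | 0.30 |

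No variant comes near 2.5. Against the exact width the stated figure is 2.5 / 0.27 ≈ 9 times too large, and against Wald 2.5 / 0.23 ≈ 11 times.

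**What 750 patients deliver**

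- Zero events: 1 − 0.05^(1/750) = 0.399%, about four times the bound at 3,000.
- 13.7%: 1.96 × √(0.137 × 0.863 / 750) = 2.46 points either side, full width 4.92.
- A true risk of 0.1%: 0.75 events expected. The chance of seeing none is 0.999^750 = 47%, against 0.999^3000 = 5% at 3,000.

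**Expected numbers by country**

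| Country | Section 6 | Section 9.4.1 |
|---|---|---|
| Norway | >3,000 | may be >3,000 |
| Finland | >3,000 | >750 |
| Sweden | possibly >3,000 | >750 |
| Denmark | 750 uncertain | >750 not anticipated |

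**The case against.** The sentence on confidence intervals closes an illustration. It overstates the uncertainty for the serious event, so it promises no precision that the study lacks. The zero-event bound, which is the part that addresses rare outcomes, is correct at 3,000, as are the expected counts. There are no a priori hypotheses, and no threshold or decision is shown to rest on the faulty figure. All of this stands, and it limits the severity.

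Section 9.5 ties its bound expressly to 3,000 and never claims it for 750. That is true of the bound. But the same section says that each final report will hold about 3,000 patients, and the rest of the protocol does not secure this.

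The 2.5 might be meant as a half-width near the 750 minimum, where 13.7% does have ±2.46. Section 9.5 states its figure for 3,000, however, and at 750 the half-width for the serious event is still only 0.23 points (Wald) to 0.37 points (exact, one event). That reading does not rescue the claim for both percentages.

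Three stronger readings are tempting and are not supported:

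- A reader might infer that the protocol does not expect 3,000 patients in Finland or Sweden. Section 6 does expect them in Finland and possibly in Sweden, and more than 750 is a floor that does not exclude 3,000. Only for Denmark is the expectation plainly lower, and the protocol discloses that.
- A reader might infer that the study-size rationale as a whole fails for rare events. It does not, because the zero-event bound is right at the size stated.
- A reader might infer that a per-patient bound mismatches the planned output. Section 9.7.3 plans incidence proportions per 1,000 persons as well as rates per person-years, so the bound serves a planned output.

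**Conclusion.** The precision statement is wrong as written. It holds for 13.7% only if read as a full width, and it is about nine times too wide for 0.1% (0.27 points, exact). This rests only on the protocol's own n and percentages and on a 95% level, and no interval method tried changes the conclusion.

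The statement of about 3,000 patients per database is broader than the protocol supports. A final analysis between 750 and 3,000 is permitted, and at the lower end the zero-event bound is 0.40%. How far this matters depends on the counts reached. A database that passes 3,000 has the bound as stated.

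The Finnish and Swedish expectations do not strictly contradict each other, but they are given against different thresholds in section 6 and section 9.4.1 and should be reconciled. Overall this is a should-fix correction of stated figures. No estimate, inclusion rule or analysis is affected.

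**What to change.** In section 9.5:

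- Replace the closing sentence with two intervals at n = 3,000: 13.7% (95% CI 12.5% to 15.0%) and 0.1% (exact 95% CI 0.02% to 0.29%).
- Limit the 3,000-patient statement to the databases expected to reach that number.
- Add what the 750 minimum delivers: zero events bounds a risk at 0.40%, and 13.7% has an interval of about ±2.5 points.

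Reconcile the expected numbers for Finland and Sweden between section 6 and sections 9.4.1.2 and 9.4.1.4.

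The cost is wording only. The drawback for the sponsor is that the stated precision becomes less favourable for databases near 750.
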